1.0 Study Summary

Study Title	Clinical evaluation of the efficacy of an intra oral rinse for patients with xerostomia
Study Design	Randomized, double –blind, placebo controlled cross over study
Primary Objective	
1. To evaluate patients’ perception of efficacy of a new currently marketed mouth rinse (HYDRAL) for xerostomia compared to a placebo mouth rinse (negative control) and another currently marketed mouthrinse (Biotene) in reducing the symptoms of xerostomia.2. To determine the efficacies on dry mouth relief and on the patient’s Quality of Life (QoL) at the beginning and end of the study.
Secondary Objective(s)	
1. To objectively evaluate the improvement of dry mouth symptoms by HYDRAL compared to the placebo and Biotene.2. To evaluate the safety of the test mouthrinse on teeth and oral soft tissues.3. To evaluate the patient’s preferences relative to the test mouthrinses.
Research Intervention(s)/ Investigational Agent(s)	Mouth rinse (HYDRAL)
IND/IDE #	N.A

Study Population	Adults males and females
Sample Size	39
Study Duration for individual participants	8 weeks
Study Specific Abbreviations/ Definitions	

2.0 Objectives*

2.1 Describe the purpose, specific aims, or objectives of this research.

Response: The objectives of this randomized double -blind placebo controlled cross over study are:

- 1) To evaluate patients' perception of efficacy of a new mouth rinse (HYDRAL) for xerostomia compared to a placebo mouth rinse (negative control) and another mouthrinse (Biotene) in reducing the symptoms of xerostomia.
- 2) To determine the efficacies on dry mouth relief and on the patient's Quality of Life (QoL) at the beginning and end of the study.
- 3) To objectively evaluate the improvement of dry mouth symptoms by HYDRAL compared to the placebo and Biotene.
- 4) To evaluate the safety of the test mouthrinse on teeth and oral soft tissues.
- 5) To evaluate the patient's preferences relative to the test mouthrinses.

2.2 State the hypotheses to be tested, if applicable.

NOTE: A hypothesis is a specific, testable prediction about what you expect to happen in your study that corresponds with your above listed objectives.

Response:

- 1) HYDRAL performs as well as or better than Biotene in reduction of the symptoms. HYDRAL performs better than the placebo rinse in reduction of the symptoms.
- 2) HYDRAL improves patient's quality of life as well as or better than Biotene. HYDRAL performs better than the placebo rinse in improvement of patient's Quality of Life (QoL)

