before coming to the screening visit. The study team will then call the patient after the Consent Form is mailed to answer any questions or concerns that they may have. The patient can mail the Consent Form back in a stamped self-addressed envelope. The withdrawal of mouthrinse can begin once the study team receives the Consent Form and notifies the patient of its receipt. Subjects will be asked about demographics, medical history, general health status and current medication usage, and the information will be recorded.

The subjects will be asked if they currently experience any problems such as burning, stinging, irritation, etc., and if so, the nature of the effect, severity and onset time (if known) will be recorded.

VAS scoring of lubrication or moisture of your mouth will be scored and unstimulated saliva flow will be measured (Inclusion Criteria). A qualified dental examiner will perform an oral soft and hard tissue examination (OST) to verify that the subjects meet the inclusion and exclusion criteria.

Following the OST exam, qualifying subject's unstimulated saliva will be collected over a 5 minutes time period and the volume measured to determine if they meet the study criteria for xerostomia. VAS question related to symptoms of xerostomia will be completed (≥ 4 cm is required for inclusion). Subjects will also be asked to refrain from eating or drinking for 1 hour prior to being examined.

If the patient meets the study criteria and has time to participate in visit 1, they may enter the study following the screening visit. If acceptable for the study, this screening visit will serve as their Visit I baseline.

Visit I

This visit will last approximately 1 hour. The following will happen at this visit: Subjects will be asked to refrain from eating or drinking for 1 hour prior to being examined. If Screening visit and Visit 1 don't happen at the same day, the study staff will update Inclusion/Exclusion Criteria, medical history and concurrent medications.

Subjects will complete VAS question (Appendix A), Xerostomia questionnaire (Appendix B) and Oral Health Impact Profile -14 (OHIP-14) (Appendix C) for the baseline information.

A qualified dental examiner will perform an oral soft and hard tissue examination (OST), unstimulated saliva flow measurement and the objective assessment of oral health condition using the standardized instrument, Revised Oral Assessment Guide (ROAG) (Appendix D). Some intraoral photographs will be taken.

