19.0 Data Management and Analysis*

19.1 *Describe the data analysis plan, including any statistical procedures. This section applies to both quantitative and qualitative analysis.*

Response: This is a randomized double-blind placebo controlled crossover study comparing the HYDRAL Oral rinse to Biotene rinse, and HYDRAL Oral rinse to placebo. A one-week wash-out period will be adopted between phases to eliminate any possible carry-over effect of a treatment from previous phase. The primary endpoint is a reduction of dry mouth symptom in VAS (0-10 scale). To control for the Type I error rate of incorrectly rejecting the null hypothesis, a two-sided significance level of 0.025 will be used. A power analysis for a crossover study estimated that with 80% power, 33 subjects will be required to detect a minimal difference in mean VAS of 0.8. To account for withdrawal and other factors (e.g. failed measurement), a total of 39 subjects will be recruited and randomized into the study.

Descriptive statistics for all subjects will be performed for background and demographic variables. Continuous variables are expressed as frequencies (n), mean +/- SD and categorical variables are expressed as frequencies (n) and percentages (%). To evaluate the primary end point, an Analysis of variance will be applied to examine the possible residual or carryover effects of treatments. If no residual effect is found, paired t test or Wilcoxon sign-rank test where appropriate, will be used to compare treatments; however, if residual effect is significant, a mixed model (with unstructured covariance matrix) will be performed with treatment, period,

and interaction of treatment and period as fixed effects to account for treatment, period, and carryover effect. For categorical variables, percent or proportion of subjects will be calculated and a Chi-square test or McNemar test will be used. All statistical tests will be conducted using SAS version 9 (SAS Institute Inc. Cary, NC).

19.2 *If applicable, provide a power analysis.*

NOTE: This may not apply to certain types of studies, including chart/records reviews, survey studies, or observational studies. This question is asked to elicit whether the investigator has an adequate sample size to achieve the study objectives and justify a conclusion.

Response: The number of subjects needed for this study with adequate power is based on a power analysis of 0.8.

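### The hypothesis that HYDRAL does as well as Biotene on VAS has no margin or decision rule, so the planned tests can confirm only the superiority limb

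*Combined protocol and SAP*

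**What the plan says.** Section 2.2 makes two different claims. Against placebo, HYDRAL is to be better. Against Biotene, "HYDRAL performs as well as or better than Biotene in reduction of the symptoms", and the second hypothesis repeats the form for "quality of life as well as or better than Biotene". The template note in the same section says that "A hypothesis is a specific, testable prediction about what you expect to happen in your study".

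Section 19.1 describes a crossover "comparing the HYDRAL Oral rinse to Biotene rinse, and HYDRAL Oral rinse to placebo". The primary endpoint is the reduction in dry mouth on a 0 to 10 VAS. On error control, "a two-sided significance level of 0.025 will be used". On size, with 80% power, "33 subjects will be required to detect a minimal difference in mean VAS of 0.8", and 39 are to be randomized.

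If no carryover is found, treatments are compared by a paired t test or Wilcoxon signed-rank test. If carryover is significant, a mixed model is used instead. Neither document section, nor any other, gives a non-inferiority or equivalence margin or a rule based on a confidence interval.

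**The concern.** The wording differs by comparator, but the analysis does not. A claim of parity needs a statement of how large a loss would still count as parity, and a test or interval that can exclude that loss. The named tests ask only whether the difference is zero. They can show HYDRAL better or worse than Biotene; failing to reject shows neither parity nor a difference.

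The comparison with Biotene is the first one listed in 19.1, and a non-significant result is a realistic outcome. The plan does not say what would then be concluded about the hypothesis in 2.2. Two things could go wrong: non-significance could be reported as support for parity, or a margin could be chosen once the results are known. The superiority limb against Biotene and the placebo comparison on VAS are not affected.

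**Working it through.** **Inputs from 19.1:** 33 evaluable subjects, 39 randomized, two-sided level 0.025, 80% power, difference 0.8. **Not given:** any SD. The plan's 33 therefore cannot be reproduced independently; it can only be solved backwards for the SD it implies.

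**Step 1: implied SD of paired differences.** For a paired t test, power = P(|T| > t*), where T is noncentral t with n−1 degrees of freedom and noncentrality λ = δ√n/SD. With n=33, t* = 2.352 (two-sided 0.025, 32 df). Setting power to 0.80 at δ=0.8 gives SD = 1.43, so λ = 0.8 × 5.745/1.43 = 3.21. The normal approximation gives 0.8 × √33/(2.241 + 0.842) = 4.596/3.083 = 1.49. I use 1.43.

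**Step 2: how often the planned test is non-significant when HYDRAL is truly worse.** The standard error is 1.43/√33 = 0.249 at n=33 and 1.43/√39 = 0.229 at n=39. For a true deficit d, λ = d/SE, and the probability of non-significance is P(|T| ≤ t*).

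| True deficit (VAS points) | n=33 | n=39 completers |
|---|---|---|
| 0.5 | 62% | 55% |
| 0.8 | 20% | 13% |

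The 20% is the complement of the plan's 80% power. The 0.5 is my choice of a smaller deficit for illustration.

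Since the SD is an assumption, here is the spread for SD 1.0 to 2.0. For a deficit of 0.5 it is 30% to 81% at n=33 and 22% to 77% at n=39. For 0.8 it is 1.5% to 51% and 0.5% to 43%. The ends of that range do not fit the plan's own 80%: at n=33 they would give 98.5% and 49% power to detect 0.8.

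**Step 3: what a parity rule could deliver at the planned size.** Suppose parity is concluded when the two-sided 97.5% interval excludes a loss as large as the margin (one-sided 0.0125). With a true difference of zero, power = P(T > t*) with λ = margin × √n/SD.

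| Margin | n=33, SD 1.43 | n=33, SD 1.0 to 2.0 | n=39, SD 1.43 |
|---|---|---|---|
| 0.8 | 80% | 98.5% to 48.7% | 87% |
| 0.5 | 38% | 69.8% to 19.5% | 45% |

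At SD 1.43, 80% power for a margin of 0.5 needs 81 evaluable subjects. The interval width shows why: its half-width at n=33 is 2.352 × 0.249 = 0.586. Even an observed difference of exactly zero would not exclude a loss of 0.5; HYDRAL would have to be observed better by about 0.586 − 0.5 = 0.086. The choice of margin can therefore decide the conclusion.

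**The case against.** The strongest reply is that the hypothesis is a disjunction. A reader might infer that it cannot be confirmed at all, but the documents do not support that: a significant result favouring HYDRAL under 19.1 would confirm the superiority limb and so the full sentence on VAS. The paired or mixed-model analysis would also yield an estimate from which an interval follows. What is missing is the margin and the rule, not an analysis. Both points stand, and the finding is limited accordingly.

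It can also be said that the harm is conditional. A reader might infer that the investigators intend to treat non-significance as parity; no section says so, and 19.1 reads throughout as a superiority plan. The percentages in the table describe a misreading that the plan leaves open, not one that it prescribes. That also stands. It does not remove the mismatch, because 2.2 puts the parity claim among the hypotheses to be tested and 19.1 supplies nothing to test it with.

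On quality of life, OHIP-14 is completed at Visit 1 ("Oral Health Impact Profile -14 (OHIP-14) (Appendix C) for the baseline information") and after each product, yet 19.1 names no test for it. A reader might fold that into this point. It is a separate gap in detail that touches the placebo hypothesis equally, and it is not part of this finding.

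**Conclusion.** The point holds for the parity limb on VAS. It rests on the text: a parity claim in 2.2, zero-difference tests in 19.1, and no margin or interval rule anywhere. It does not depend on the numbers.

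The size is illustrative. It assumes a simple paired t analysis and an SD of differences of 1.43, back-solved rather than stated. On that basis non-significance at n=33 would pass a true deficit of 0.5 about 62% of the time and one of 0.8 about 20% (55% and 13% with 39 completers).

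Two further inferences are not supported. Nothing here shows that 33 or 39 is wrong for the superiority comparisons. And the 0.8 in 19.1 is a difference to detect; it cannot be taken as a margin without its own justification. The matter should be fixed, since it changes what the trial may conclude about Biotene and the simplest repair is wording.

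**What to change.** Choose one of two routes.

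**(a) Wording only.** In 2.2, restrict the Biotene hypotheses, for symptoms and for quality of life, to superiority. In 19.1, state that a non-significant difference between HYDRAL and Biotene will not be reported as parity.

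**(b) If parity is to be claimed on VAS.** Fix and justify a margin before unblinding. Conclude parity only if the two-sided 97.5% confidence interval for HYDRAL minus Biotene excludes a loss as large as the margin. Define the direction: for VAS reduction, where higher is better, the lower limit must lie above minus the margin; for post-treatment VAS, where lower is better, the upper limit must lie below the margin. State the non-inferiority power at the planned N. Apply the restriction in (a) to the quality-of-life hypothesis.

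Route (a) costs two edits and no subjects. Route (b) costs a margin justification and a recheck of N: under the assumed SD the planned size would serve a margin near 0.8, but a margin of 0.5 would need 81 evaluable subjects. Under either route the claim against Biotene becomes stricter.

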3.0 Scientific Endpoints*

2.1 Describe the scientific endpoint(s), the main result or occurrence under study.

NOTE: Scientific endpoints are outcomes defined before the study begins to determine whether the objectives of the study have been met and to draw conclusions from the data.

*Include primary and secondary endpoints. Some example endpoints are: reduction of symptoms, improvement in quality of life, or survival. Your response should **not** be a date.*

Response: The primary endpoint is a reduction of dry mouth symptoms

4.0 Background*

4.1 Provide the scientific or scholarly background, rationale, and significance of the research based on the existing literature and how it will contribute to existing knowledge. Describe any gaps in current knowledge. Include relevant preliminary findings or prior research by the investigator.

Response: Currently, the prevalence of dry mouth varies widely among the general population. When asked, 14–46% of the adult population complains about dry mouth problems, women more than men [1]. Xerostomia is generally defined as a subjective feeling of dry mouth, often the result of hyposalivation caused by different medical issues. All grades of xerostomia may impact on oral health and quality of life [2]. Long-term causes of hyposalivation include chronic diseases (diabetes, Sjögren’s syndrome, Parkinson’s disease, rheumatoid arthritis, etc.), illness of the parotid glands, malignancies in the head and neck region and their treatment, as well as head and neck surgery or anamnestic radiation. Another underrated main cause of xerostomia in the general population is medication-induced xerostomia [3]. Older age in combination with a large number of prescribed drugs ranks as an important activator for xerostomia [4–6]. The clinical oral effects of xerostomia are many and include difficulties in speaking, swallowing or eating, a reduced or altered taste sensation, atrophy of mucosal tissue with pain, demineralization of the teeth, and often occurrence of secondary infections of oral tissues [7].

Yet there is almost no evidence in the literature regarding treatment of this special patient population with medication-induced xerostomia with symptom-relieving products, or evidence-based guidelines as to which products can be recommended to patients and how effective they are [8]. The efficacy of therapies is mainly described in populations with post-radiotherapy xerostomia [9–13]. In this study, we intend to investigate and compare the efficacy of GUM Hydral and Biotène Oral balance.

4.2 Include complete citations or references.

Response:

[1]. Sreebny LM (2000) *Saliva in health and disease: an appraisal and update. Int Dent J 50:140–161*

[2]. Davies AN (2000) *A comparison of artificial saliva and chewing gum in the management of xerostomia in patients with advanced cancer. Palliat Med 14:197–203*

5.0 Study Design*

- 5.1 Describe and explain the study design (e.g. case-control, cross-sectional, ethnographic, experimental, interventional, longitudinal, observational).

Response: Randomized double -blind placebo controlled cross over study.
Randomization-Patients will be assigned to the study product using a random numbers table. Both the placebo rinse and the “active “test rinses” will be provided by the sponsor in similar bottles labeled with a code label for each bottle. The code and patient numbers will be kept in a sealed cabinet in [name]. The code will only be broken if there is need to identify a patient with adverse effects which may be attributed to the rinse they were given.

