They will then be given their assigned product to use four times daily for two weeks. Subjects will maintain a daily diary (Appendix E) of their product usage and any oral effects they experience and will answer all diary questions. Compliance will be assessed by subject diary and measurement of when unused portion is returned to the clinic.

The subjects will be instructed not to use any other xerostomia products for the duration of the study and to follow their normal oral hygiene procedures. All subjects will be provided with a soft toothbrush and regular fluoride toothpaste to use during the study. Subjects will be scheduled to return in approximately 2 weeks, and will be instructed to refrain from eating and drinking for approximately 1 hour prior to their next visit. They will be advised to follow the instructions carefully and return to the study center with their assigned mouthrinse, and diary after 2 weeks for their next examination. Subjects will receive a reminder call prior to Visit 2.

Visit 2

After 2 weeks, subjects will return to the office to return their diary. This visit will last approximately 1.5 hour. The following will happen at this visit: The study staff will update of medical history and concurrent medications. Adverse experiences will be noted and recorded during the study.

The study examiner will perform ROAG(Appendix D) to assess the subject's oral health condition.

Subjects will complete VAS question (Appendix A), Xerostomia questionnaire (Appendix B) and OHIP-14 (Appendix C) for after 2 weeks use of the first product. At Visit 2, they will also complete Product Performance and Attributes Questionnaire for the first product (Appendix F).

A qualified dental examiner will perform OST, unstimulated saliva flow measurement and the objective measurement of xerostomia symptoms (Appendix D). Some intraoral photographs will be taken.

Subjects will then remain in the study center for 60 minutes to evaluate whether their mouth feels moist or lubricated, xerostomia relief by questionnaire at 5, 15, 30, 45 and 60 minutes after the in-office use of their assigned product rinse (Appendix G).

Visit 3

After a 1-week washout, subjects will return to the office to begin the second period of the study, using the same study procedures and be assigned the alternate treatment rinse as in Visit 1.

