At the end of Visit 4 (examination for the second product) they will go through a 1 week wash out period and then return for Visit 5 (baseline for the third product) and study will be completed in visit 6.

12.2 Describe what data will be collected.

NOTE: For studies with multiple data collection points or long-term follow up, consider the addition of a schedule or table in your response.

Response: The various data collection points are shown in Table 1 (Study Schedule).

Events	Screening	Visit 1	Visit 2	Visit 3	Visit 4	Visit 5	Visit 6
		First product		Second product		Third product	
Informed Consent, Demographics, Inclusion/Exclusion Criteria, Medical History, Concurrent meds	X						
Demographics Questionnaire	X						
Oral Soft/Hard Tissue Exam & Photos		X	X	X	X	X	X
Update of Inclusion/Exclusion Criteria, Medical History and Conmeds		X	X	X	X	X	X
Unstimulated saliva flow	X (<0.2)	X	X	X	X	X	X
VAS	X (>=4)	X	X	X	X	X	X
Questionnaires (Xerostomia, QoL)		X	X	X	X	X	X
Objective xerostomia endpoint (ROAG)		X	X	X	X	X	X
Product Distribution		X	X	X	X	X	X
Diary Disbursement		X		X		X	
Compliance Check			X		X		X
Product Attribute Questionnaire			X		X		X
Immediate Post-Rinse Evaluation			X		X		X
Adverse Events			X	X	X	X	X

12.3 List any instruments or measurement tools used to collect data (e.g. questionnaire, interview guide, validated instrument, data collection form).

Include copies of these documents with your submission.

Response:

- a. Demographics Questionnaire
- b. Intraoral camera
- c. Medical History
- d. VAS question (Appendix A),
- e. Xerostomia questionnaire (Appendix B)
- f. Oral Health Impact Profile -14 (OHIP-14) (Appendix C)
- g. Revised Oral Assessment Guide (ROAG) (Appendix D)
- h. Daily Diary (Appendix E)
- i. Product Performance and Attributes Questionnaire for the first product (Appendix F)
- j. Immediate Post-Rinse Evaluation (Appendix G)
- k. Oral soft and hard tissue examination form
- l. *Unstimulated saliva flow measurement form*
- m. *Adverse Events form*

12.4 Describe any source records that will be used to collect data about subjects (e.g. school records, electronic medical records).

Response: No source records will be used to collect data about subjects.

12.5 Indicate whether or not **individual** subject results, such as results of investigational diagnostic tests, genetic tests, or incidental findings will be shared with subjects or others (e.g., the subject's primary care physician) and if so, describe how these will be shared.

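### No sequence set or order balance is stated for the three-period crossover, and the default paired test has no period term, so a period effect would cost precision and power

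*Combined protocol and SAP*

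**What the plan says.** Section 5.1 gives the whole allocation method in one sentence: "Patients will be assigned to the study product using a random numbers table". It speaks of a product, not a sequence of products, and names no block size or restriction. Section 12.1 sets out three periods (Visits 1–2, 3–4 and 5–6). It says only that at Visit 3 subjects will "be assigned the alternate treatment rinse as in Visit 1", which does not define an order among three products. Section 22.3 replaces a withdrawn subject with one given the same treatment, and refers to a third party who supplied the randomisation codes.

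Section 19.1 describes the trial as "comparing the HYDRAL Oral rinse to Biotene rinse, and HYDRAL Oral rinse to placebo", and states that "a two-sided significance level of 0.025 will be used". On sample size it says that "with 80% power, 33 subjects will be required to detect a minimal difference in mean VAS of 0.8", and that "a total of 39 subjects will be recruited and randomized into the study". If the carryover test finds nothing, products are compared by "paired t test or Wilcoxon sign-rank test where appropriate". Period enters only through a mixed model, which is used only if carryover is significant.

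**The concern.** In a crossover, each product should occur equally often in each period, or the analysis should adjust for period, and preferably both. As written, the plan secures neither on its default path.

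A period effect is plausible here. Entry requires a VAS score of at least 4 (Section 8.1), and the screening visit may serve as the Visit 1 baseline (Section 12.1). The first baseline is therefore selected to be high, and no such threshold applies at Visits 3 and 5. If the outcome is change from each period's baseline, regression to the mean would add apparent improvement to whichever product is taken first. If more subjects take HYDRAL first than placebo first, part of that shift ends up in the HYDRAL–placebo difference, and the unadjusted paired test cannot remove it. Even without a net imbalance, the shift widens the spread of the individual differences and so weakens the test.

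**Working it through.** **The plan's own figure.** The 33 cannot be reproduced, because no SD is given. Solving n = [SD × (z(0.9875) + z(0.80)) / 0.8]² for n = 33 gives SD = 0.8 × √33 / (2.241 + 0.842) = 1.49. A t-based calculation gives 1.42 to 1.43. I assume 1.45. The step from 33 to 39 matches a 15% loss (33 / 0.85 = 38.8, rounded up), but the rate is not stated.

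**Imbalance if assignment is unrestricted (assumption: six orders equally likely, n = 39).** Each subject adds +1 to the HYDRAL-first minus placebo-first count with probability 1/3, −1 with probability 1/3, and otherwise 0.
- SD of the count = √(39 × 2/3) = √26 = 5.1. In simulation it is 5 or more in absolute value in 38% of trials, and 9 or more in about 9.5%.
- Every product falls 13 times in every period in about 0.06% of trials. Some count is off 13 by 4 or more in 75%.

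**Effect on the estimate.** Let Period 1 scores be shifted by s (assumed 0.5 or 1.0 VAS units). The error in HYDRAL minus placebo is s × count / 39, with SD s × 5.1 / 39 = 0.131s, that is 0.065 or 0.13. By symmetry the same holds for HYDRAL minus Biotene. The SD of the estimate is √(1.45²/39 + (0.131s)²):
- s = 0: √0.0539 = 0.23
- s = 0.5: √(0.0539 + 0.0043) = 0.24
- s = 1.0: √(0.0539 + 0.0171) = 0.27

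**Power for a difference of 0.8, two-sided 0.025, n = 39 (simulation).**

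| Assumed Period 1 shift | Unrestricted, paired t | Blocked, paired t | Blocked, period in model |
|---|---|---|---|
| 0 | 0.86 | 0.86 | 0.87 |
| 0.5 | 0.84 | 0.84 | 0.87 |
| 1.0 | 0.74 | 0.77 | 0.87 |

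As a check on the second column, adding the period variance to the SD of a difference gives √(1.45² + 2s²/3) = 1.51 and 1.67. The noncentral t then gives power of 0.83 and 0.75, within 0.01 of the simulated values. With period in the model but no blocking, power is about 0.86. At n = 33, the unrestricted paired t has power 0.79 with no shift, and 0.75 and 0.66 with shifts of 0.5 and 1.0.

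**A harsher assumption.** With a linear drift of 0.5 or 1.0 per period and n = 39, unrestricted assignment with the paired t gives 0.78 and 0.56. With blocking and period in the model it is 0.87 and 0.88.

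**Type I error.** Under unrestricted assignment the paired t stays near nominal (0.023 to 0.027 against 0.025) and the mean estimate is not shifted. Under blocking without a period term it becomes conservative (about 0.02 and 0.01 for shifts of 0.5 and 1.0). The balance removes the error from the estimate, but the test still counts period variation in its standard error.

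**Blocking arithmetic.** 39 / 3 = 13 blocks, each a complete 3 × 3 Latin square, puts each product 13 times in each period. Each square contains three of the six ordered predecessor pairs, twice each. With 7 blocks of one square and 6 of the other, pairs occur 7 × 2 = 14 or 6 × 2 = 12 times.

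**The case against.** A reader might infer that the trial uses simple randomisation. The documents do not say so. A random numbers table can also drive permuted blocks or a draw among listed sequences, and Section 22.3 shows that a third party supplied codes, so a balanced list may exist. What stands is that the sequences and any restriction are unspecified.

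A reader might also infer that the primary comparison is biased or its type I error inflated. It is not. Random order makes the period contribution zero on average, and the paired t already carries it in its variance. What remains is chance error in the one trial that is run, and lost power.

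It is fair to say that a balanced list alone achieves little. With the unadjusted test it gains at most about three power points here. It is also fair that the size of any period effect is unknown. Section 19.1 speaks both of a reduction in VAS and of a difference in mean VAS. If the outcome is the end-of-period score, regression from the entry threshold singles out Period 1 much less. At a shift of 0.5 the loss is only two or three points.

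Finally, blocks of three are more predictable than an unrestricted list. It would be tempting to dismiss this by saying that the list is held off site, but Sections 5.1 and 20.1 keep the code in a sealed cabinet and in the investigator's locked cabinet. The coded bottles are the main safeguard.

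**Conclusion.** The point holds as a design weakness that should be corrected. No balance of product order is stated, and the default test ignores period. If assignment is unrestricted, imbalance at n = 39 is close to certain. The cost is power: from 0.86 to about 0.84 or 0.74 for Period 1 shifts of 0.5 or 1.0, and to 0.78 or 0.56 under linear drift of the same size per period. With no period effect there is no loss.

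These figures rest on assumptions that the documents do not supply: SD 1.45, the size and shape of the period effect, unrestricted allocation, complete data and normal errors. The Wilcoxon alternative was not simulated. The adjusted model pools residual variance over the three products, which accounts for the small gain even with no shift.

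**What to change.** 1. In Section 5.1, list the six sequences and state that subjects are randomised to a sequence, with each product planned to fall 13 times in each period. Build the list as 13 blocks of three from both 3 × 3 Latin squares, 7 blocks of one and 6 of the other, in random order. Predecessor counts are then nearly balanced (14 v 12), not exactly so, since 39 / 6 = 6.5.
2. In Section 22.3, say that a replacement inherits the whole sequence of the subject replaced.
3. In Section 19.1, make the primary comparison a model with treatment and period as fixed effects, whatever the carryover test shows. If only one change can be made, make this one.
4. Keep the list with the third party who supplies the codes. Put the block details in that party's randomisation specification and not in text that site staff read.

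The cost is a new list before first enrolment and a few sentences of text, with no added subjects or visits. The downsides are slightly greater predictability, and that exact period balance holds only with complete data. The period term covers the imbalance that withdrawals leave.
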